STUDY OUTCOMES	
Primary Feasibility Outcome: Time to enroll 52 patients
 
Secondary Feasibility Outcomes
 
 • Feasibility: proportion consenting to participate; proportion receiving allocated treatment; proportion completing laboratory tests, FACIT-fatigue scale, side effects questionnaire; adherence 
Secondary Clinical Outcomes
 
 • Mean hemoglobin increment at 4 and 12 weeks • Proportion with complete hemoglobin response at 4 and 12 weeks • Change in ferritin, serum iron and TSAT at 12 weeks • Quality of life (FACIT-fatigue scale) at 4, 8 and 12 weeks • Gastrointestinal adverse effects at 4, 8 and 12 weeks • Need for escalation in therapy • Proportion with a drop in hemoglobin of 10 g/L or more at 4 and 12 weeks
STATISTICAL ANALYSIS	
The results of this pilot trial will be used to assess the feasibility and inform the design of the definitive trial. We will present point estimates of feasibility outcomes with 95% confidence intervals.
 
An intention-to-treat analysis will be performed on all patients randomized for the secondary clinical outcomes. A per protocol analysis will be conducted for patients who have taken at least 90% of the prescribed doses.

[figure not shown]

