5.4.3 Prior and Concomitant Medications

Throughout the study duration, and two weeks leading up to randomization, patients are not permitted to receive other sources of iron supplementation, including but not limited to, other oral ferrous tablets and intravenous iron therapy.

Patients should be advised not to take oral iron within 2 hours of antibiotics, bisphosphonates³⁹, levodopa, methyldopa⁴⁰, mycophenolate mofetil⁴¹, or thyroid medication⁴².

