8.2 Final Analysis Plan

The results of this pilot trial will be used to assess the feasibility and inform the design of the definitive trial. We will present point estimates of feasibility events, including enrolment, adherence to protocol and accrual, as proportions with 95% confidence intervals. We will present continuous data as means and standard deviations, or medians and inter-quartile ranges, as appropriate.

An intention-to-treat analysis will be performed on all patients randomized for the secondary efficacy outcome. A per protocol analysis will be conducted for patients who have taken at least 90% of the

prescribed doses. Subgroup analysis will be performed on the stratified groups with hemoglobin 100g/L or greater and hemoglobin less than 100g/L. Additional subgroup analyses will include: patients with ongoing bleeding (WHO grade 2 or higher) vs no bleeding; and normal vs. increased CRP (based on the normal range).

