10.0 CRITERIA FOR WITHDRAWAL AND DISCONTINUATION FROM STUDY

Patients will be followed until 12 weeks or until there is an escalation of therapy as defined by need for: alternative oral iron therapy (including if a participant in the every other day group escalates to daily iron), need for intravenous iron, need for transfusion, or a visit to emergency department related to anemia.

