10.1 Early Termination and Reasons for Withdrawal

Patients may find that they are not able to continue in the study due to intolerable side effects from the oral iron despite simple measures to address the side effects. Patients are permitted to withdraw consent at any time if they desire and will not undergo further trial investigations if they do so.

Additionally, patients who become pregnant during the course of the study will be stopped from using the study medications and withdrawn from the study. Other reasons for withdrawal include use of

intravenous iron, use of blood transfusion, any deviation from inclusion/exclusion criteria and serious adverse events (as described in section 9.3).

Participants withdrawing from the study should be contacted by the study research team requesting a final visit and to follow up with any unresolved adverse events. Once withdrawn from the study, no further study procedures or evaluations should be performed, or additional study data collected. However, every effort should be made to obtain permission to document the reason for withdrawal and to collect participant outcomes, such as survival data up to the protocol-described end of participant follow up period, where possible. Any data collected prior to the withdrawal of consent may be retained and used by the sponsor. If the patient withdraws from the study, the research team will notify the patient's referring physician.

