10.2 Data Collection and Follow-up for Withdrawn Participants

Patients will be asked to continue with follow-up quality of life assessment and laboratory tests. It is important to continue to follow these patients and capture outcomes that occur once they have discontinued study intervention to determine feasibility. Through telephone calls and emails, every effort will be made to obtain permission to document the reason participants withdrew consent and to continue collecting the quality of life assessments and laboratory values previously mentioned. Patients who have completed at least 90% of the prescribed doses will be included in the per-protocol analysis.

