5.3.3.3 packaging	Removed 120 from the sentence “standard package of 120 vitamin C pills that are to be taken along with the study drug”.	Participants receive either ‘45’ or ‘90’ tablets in their packaging depending on their randomization schedule. Standard package does not include 120 vitamin C pills.
5.4.1.1 screening and enrollment will occur within 1 week of randomization	Removed ‘response’ for both IV and oral iron.	Lack of response to oral iron is already captured in the eligibility checklist. Response to IV iron does not impact this study.
5.4.1.2 Baseline laboratory assessment	Added “screening bloodwork can be used for the baseline laboratory assessment”	To clarify that the screening bloodwork can be used for baseline laboratory assessment.
5.4.2.2 week 4	Added “medication history (to confirm if any new medications or discontinued any previous medications)”.	To clarify that the study team will be asking the participants if they have started any new medication at each visit during the trial.
5.4.2.3 week 8	Added “medication history (to confirm if any new medications or discontinued any previous medications)”.	Same as 5.4.2.2
5.4.2.4 Week 12 Final study visit	Added “medication history (to confirm if any new medications or discontinued any previous medications)”.	Same as 5.4.2.2
5.4.4 participant compliance monitoring and assessment	Added “if a patient misses a pill, they will continue with the next dose as directed on the calendar and not to double up dosing”.	To specify the procedure if a participant misses a pill. Also to clarify that missing a pill is not considered a protocol violation.
8.1 sample size and sample size justification	Added “the trial will proceed until there are 52 enrolled patients and at least 36 patients who complete the trial to 13 weeks without dropping out”.	To specify the number of patients needed in order for the trial to be considered complete.
Appendix B	Added “completed by, date and reviewed by and date”	To record the personnel completing and reviewing the PBAC score calculation.

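### The per-protocol set rests on a single 90%-of-doses rule, so patients who were ineligible, took prohibited iron or were sampled after rescue can remain in the per-protocol hemoglobin analysis

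*Combined protocol and SAP*

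**What the plan says.** The per-protocol rule appears three times, always with the same single condition.

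- Protocol Summary: "A per protocol analysis will be conducted for patients who have taken at least 90% of the prescribed doses". Section 8.2 repeats this.
- Section 10.2, under the heading for withdrawn participants: "Patients who have completed at least 90% of the prescribed doses will be included in the per-protocol analysis". The same section asks these participants to go on with quality-of-life and laboratory follow-up.

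Other sections bear on the rule but are not tied to it.

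- Section 5.4.3: "patients are not permitted to receive other sources of iron supplementation, including but not limited to, other oral ferrous tablets and intravenous iron therapy". No consequence for the analysis is given.
- Section 10.1 includes among the reasons for withdrawal "intravenous iron, use of blood transfusion, any deviation from inclusion/exclusion criteria", and says that no more study data are gathered after withdrawal.
- Section 10.0: "Patients will be followed until 12 weeks or until there is an escalation of therapy". Escalation there covers alternative oral iron, a move from every other day to daily, intravenous iron, transfusion and an anemia-related emergency visit. Section 5.4.2.2 likewise ends assessments after escalation following a week 4 hemoglobin drop.
- Section 7.2 item 6 measures adherence by pill count, as total doses minus missed doses, divided by total doses.
- Section 5.4.5 says only that deviations will be considered in the analysis as needed.

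**The concern.** A per-protocol comparison should show what happens when eligible patients follow their assigned regimen. A lower limit on doses does not secure that. It says nothing about eligibility, other iron or rescue, and by stating the rule under withdrawn participants, 10.2 keeps withdrawal from removing anyone.

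The design is described as non-inferiority (2.2 and 5.1), with a 5 g/L margin in 8.1. Hemoglobin raised by rescue or other iron in the every-other-day arm moves the difference toward non-inferiority. The intention-to-treat analysis covers all randomized patients, so a per-protocol set that keeps the same affected values is a weak check on it. The pilot is also meant to inform the definitive trial, where the definition would matter more.

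**Working it through.** **The plan's own figure.** The Table 2 row matching the planned size has SD 5, true difference 0, margin 5, 90% power and one-sided 5%. Per arm, 2 × (1.645 + 1.282)² × 5²/5² = 17.1, so 18. The total is 36, and 36/0.70 = 51.4, so 52. Both figures reproduce. The 18 per arm is used below.

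**When 90% is reached.** Take prescribed to mean the full 12 weeks with no missed doses.

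| | Daily | Every other day |
|---|---|---|
| Doses in 12 weeks | 84 | 42 |
| 90% | 75.6, so 76 | 37.8, so 38 |
| Day reached | 76 | 1 + 2 × 37 = 75 |
| Days left to nominal day 84 | 8 | 9 |
| Days left to day 91 (end of window) | 15 | 16 |

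A patient who stops study tablets at intravenous iron or transfusion qualifies only if this happens in those last days. If prescribed means doses due up to withdrawal, an adherent patient qualifies whenever rescue occurs. The plan does not say which is meant, nor how a step-down under 5.3.4 changes the denominator.

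**Who the rule admits.**

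- *Prohibited oral iron alongside study tablets.* The patient can reach 90% in the ordinary way. 10.1 does not name this as a reason for withdrawal.
- *Ineligible patients.* 10.1 makes an eligibility deviation a reason for withdrawal, but one found late, after 90% of doses, leaves the patient in the set.
- *Intravenous iron or transfusion before the week 12 sample.* The later hemoglobin is not collected under 10.0 and 10.1, but is requested under 10.2. The sections cannot all be followed.

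**Size if rescued values enter.** The documents give no rescue effect. Assume a gain of 10 to 20 g/L and 18 patients per arm. The arm mean then shifts by (number rescued × gain)/18:

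- one patient: 10/18 = 0.56 to 20/18 = 1.11 g/L
- two patients: 20/18 = 1.11 to 40/18 = 2.22 g/L

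The margin is 5 g/L. A gain of that size within 8 to 9 days is an assumption, so these are illustrations.

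**Extra tablets.** The Summary of Changes entry for 5.3.3.3 gives 45 or 90 "tablets in their packaging depending on their randomization schedule". It does not say clearly whether these are iron or vitamin C tablets. Assume 45 iron tablets for the every-other-day arm.

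- Daily use from day 1 empties the bottle on day 45. The pill count shows no missed doses, so 7.2 item 6 gives 100%.
- Scheduled days are 1, 3, …, 83. Those up to day 45 number 23, and 23/42 = 55%.
- With daily use from day 29 (14 doses already taken), the other 31 tablets last to day 59. Scheduled days covered are 30, and 30/42 = 71%.
- The most that dispensed tablets can show is 45/42 = 107% (daily arm 90/84 = 107%).

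The pill count misses this departure and the diary schedule detects it.

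**The case against.** The strongest reply is that the protocol already limits the problem. Follow-up ends at escalation (10.0), assessments stop after a week 4 escalation (5.4.2.2), and data collection ends at withdrawal (10.1). Under those sections a hemoglobin value after rescue would not normally exist. This stands as a limit on size. It does not settle the matter, because 10.2 asks for the tests those sections would stop, and none of the three says who belongs to the per-protocol set.

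A reader might infer that all rescued patients count as per protocol. They do not: the sentence in 10.2 is conditional on 90%, and on the full-course reading few rescued patients would meet it.

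A reader might also infer that every-other-day patients who move to daily dosing stay in the set and raise that arm's week 12 mean. The documents do not show this. With about 45 tablets for 42 scheduled doses, total iron is nearly fixed and the tablets run out early. More tablets would need new supply, which is escalation under 10.0. Section 5.4.4 also compares the pill count with the number due. What remains is the scoring fault in 7.2 item 6.

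Finally, excluding values after rescue has its own bias. It removes treatment failures, and if these cluster in the every-other-day arm the result again moves toward non-inferiority. This stands and has to be reported with the analysis.

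**Conclusion.** The point holds in limited form. The only stated criterion admits ineligible patients, users of prohibited iron, and week 12 values taken after intravenous iron or transfusion, provided 90% is reached. The non-study oral iron route is the most open. The rescue route is about 8 to 9 days at nominal day 84, and 15 to 16 only if the sample is taken on day 91. It widens considerably if prescribed means up to withdrawal. The pill-count formula can score 100% for a patient who covered about 55% of scheduled days, assuming a 45-tablet supply.

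Severity is low to moderate. The primary outcome is time to enroll, hemoglobin is secondary, an intention-to-treat analysis is planned, and 8.2 names no per-protocol hypothesis test. Planned sample size is unaffected. That the definitive trial will carry the definition over is a risk; the documents do not say that it will.

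**What to change.** In the Protocol Summary, 8.2 and 10.2:

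1. Define the per-protocol set as randomized patients who met the eligibility criteria and took at least 90% of doses on their assigned scheduled days, over a stated 12-week denominator (84 or 42). Use the diary, checked against the pill count. A percentage cap on tablets adds little: a 110% limit, for example, could exclude nobody when dispensed tablets allow at most 107%.
2. Exclude from the per-protocol analysis hemoglobin values taken after intravenous iron, transfusion, other prohibited iron or a regimen increase. Keep earlier values.
3. Make the last sentence of 10.2 subject to this definition.
4. Reconcile 5.4.2.2, 10.0 and 10.1 with 10.2 on what is collected after escalation or withdrawal. Which rule applies is for the sponsor and investigators to decide.
5. Report the number of patients and values excluded by arm and reason, and read the result beside the intention-to-treat analysis.

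The cost is wording. Diary, pill count, medication history and escalation are already collected. The set becomes slightly smaller, and it loses treatment failures, which is why item 5 is needed.

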11.0 ETHICAL ISSUES

11.1 Ethical conduct and ethical issues

Approval for patient accrual must be obtained from research ethics board (REB) at the study center before patient recruitment can begin. Any additional correspondence with REB must be maintained by the research coordinator/assistant at each participating site.

11.2 Informed Consent

Study personnel will approach the MRP for permission to approach the patient or ask that they introduce the study to the patient. With permission, the research coordinator will then approach potentially eligible patients to introduce the trial and conduct the informed consent discussion. By being invited into the patient's circle of care with the permission of the MRP, study personnel will screen patients for exclusion criteria by asking about the patient's medical history and reviewing their bloodwork that will be taken as a standard of care when visiting the MRP. Patients interested in participating and meeting both inclusion and no exclusion criteria will be given an Informed Consent Form. This discussion will include the rationale for the study, the anticipated risks and benefits of participation, and their rights as a study participant (including withdrawal at any time). Capable participants will be offered an opportunity to ask questions and consult with their family and/or their physician before enrollment. If the patient is deemed medically incapable, study personnel will approach the patient's physician to determine if it is safe to delay treatment while a substitute decision maker is identified and approached. As the initiation of oral iron is not urgent, there will be enough time to assess the patient for inclusion in the study before initiating treatment. The subject will be invited to participate and must provide informed consent prior to any study related procedures. One signed copy of the informed consent will be placed in the participant's medical record, another copy given to the participant and the original kept in the study file with the research coordinator. Once the subject is enrolled, his/her family physician will be informed about his/her participation in the study. If the participant does not wish to participate, the reason for declining will be documented and the patient will be considered a screening failure (failure to provide informed consent).

12.0 STUDY ADMINISTRATION

The coordinating site will be Sunnybrook Health Sciences Centre. The site research coordinators will be responsible for trial coordination, site training, site start-up/activation, document management, supply management, database development, data management and statistical analysis. Study data and patient surveys will be entered and maintained on a secure password protected database developed using REDCap (www.projectredcap.org) and will be accessible via the Internet for data entry purposes.

12.1 Arrangements for day-to-day management of the trial

The research coordinator will be responsible for this aspect of the study, including system checks, maintenance, and data back-up. Patient data will be collected monthly and entered into the electronic case report forms. Data queries will be generated monthly for participating sites. A bi weekly status report will include an update on the recruitment and status of all randomized patients. Monthly to bi-monthly audit and feedback meetings will be held for participating sites. Protocol violations will be audited at each site and recorded on designated Protocol Violation Forms.

Clinical research coordinators at each site will work with site investigators on start-up activities (REB applications; study contract; organizing study materials; local in-services). Thereafter, research coordinators will screen, consent and enrol patients, complete case report forms, and respond to data queries.

12.2 Quality Assurance

Study data will be maintained on a secure password protected database accessible to study centres from the world-wide-web. Each centre will enter data for the study participants enrolled at their site. Quality control will be ensured by oversight by the research coordinator at Sunnybrook Research Institute, who will review the electronic data for all participants on a regular basis for completeness and consistency.

Quality and completeness of data entry will be reviewed as soon as possible after data entry, within five business days of data entry for the first five participants randomized at each site, and within 15 days of data entry thereafter. Data queries generated by identification of incomplete or inconsistent data will be raised and should be resolved by the study coordinator or PI in a timely manner. Corrections or changes in the data management system are tracked with the retention of the original data and the corrected data with the date of data entry and submitting personnel.

13.0 SITE MONITORING, auditing and inspecting

13.1 Site Monitoring Plan

Site monitoring is conducted to ensure the safety of human study participants and the protection of their rights and well-being. Monitoring also verifies that collected study data is accurate, complete and verifiable by source documentation and that the study is conducted in accordance with the protocol and operating procedures.

Monitoring for this study is the responsibility of the sponsor, Sunnybrook Research Institute. The delegated monitor will evaluate study processes and documentation based on the approved protocol/amendment(s), of the Natural Health Product Regulations, the International Conference on Harmonisation (ICH), E6: Good Clinical Practice guidelines (GCP) and institutional policies.

The extent and nature of monitoring is outlined in the Monitoring Plan. The monitoring plan specifies the frequency of monitoring, monitoring procedures, the level of site monitoring activities, and the distribution of monitoring reports. Monitoring activities will be performed both in person and remotely.

Reports of findings identified during monitoring activities will be provided to sites detailing any required actions. Documentation of monitoring activities and findings will be provided to the site study team and the study QI. The institution and/or local REB reserves the right to conduct independent audits as necessary.

The Investigator is responsible for ensuring monitors and/or quality assurance reviewers are given access to all study-related documents noted above and study related facilities (e.g. pharmacy, diagnostic laboratory, etc.), and have adequate space to conduct the monitoring visit or audit.

13.2 Monitoring Plan

The monitoring plan will consist of the following: 1) A site initiation visit for non-Sunnybrook sites will be conducted prior to the commencement of the study to ensure both sites are appropriately aware and prepared to conduct study procedures to institutional, provincial and Health Canada standards. During this initiation teleconference, any issues that may be raised will be adequately dealt with and recorded in a report for future reference. 2) A site monitoring visit will be conducted by Clinical Trial Services or its delegate. This visit will involve reviewing study procedures, participant data and Health Canada regulation compliance. A report will be generated based on the visit which addresses any changes that need to be made or considered for appropriate regulatory compliance and patient safety.

13.3 Auditing and Inspecting

The investigator will provide direct access to source data/documents for the purposes of study-related monitoring, audits, and inspections by the REB, the sponsor, and applicable regulatory bodies. The investigator will permit the review of all study related documents (e.g. source documents, regulatory documents, data collection instruments, study data etc.) and will ensure access to applicable study-related facilities (e.g. pharmacy, diagnostic laboratory, etc.).

